The survey will be conducted online using established methods for Web-based surveys.¹⁰² To enhance the survey response, we will employ the well-established method developed by Dillman.¹⁰³ First, all members of the sample will receive a personalized, advanced notice email. This helps to identify the purpose of the survey and establish its legitimacy. Second, approximately one week after the advance email is sent, all members of the workgroup receive the survey link. In all cases, the replies to the surveys will be anonymous. Third, approximately one week after completion of the PSAT, a follow-up email will be sent to all members of the sample. It will thank those who have already responded and request a response from those who have not yet responded. Finally, once data collection is closed, the workgroup members will receive a detailed sustainability report that includes their responses and an aggregated score for the program. For intervention states, this report will serve in the assessment and planning phases. All correspondence will come from WU and the TCN (an important professional association for our sample). The CDC has also agreed to allow us to participate on the OSH Program Service Branch calls to make CDC program officers aware of their state’s participation and for promotion of our study. We have had previous success with online administration of surveys including the PSAT. Response rate for PSAT administration across the six TC states was 86% (123 out of 143). In another study, in which we administered an email survey among all 50 state TC managers in three waves, with an overall response rate of 97%.^{51,78} In addition, we have years of experience and building partnerships with state TC programs and CDC-OSH.

Program record abstraction

A review and abstraction of state level TC program public records will be performed for all 24 states at three time points- baseline and at the annual CDC progress reporting time (June) in years

2 and 3. This will help in evaluating the impact of the training intervention on the capacity for sustainability and institutionalization of the TC program within the organization.

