In order to collect additional organizational metrics, a key informant interview and survey will be conducted with state program managers. These will be performed for all 24 states at three time points- baseline and in June during years 2 and 3. This will help in evaluating the impact of the training intervention on the capacity for sustainability and institutionalization of the TC program within the organization.

Step 1: Identifying relevant measures. Relevant state-level sustainability metrics will be identified within the 24 selected states from various sources, including CDC Best Practices, ALA State of Tobacco Control, empirical literature, and consultation of our advisory group.

Step 2: Key Informant Interview and Survey. TC program managers will be contacted to complete a phone interview and survey. The interview and survey will only collect organizational metrics not collected in reporting records, and no personal information will be collected. We will record phone interviews to ensure comprehensive analysis by trained abstracters. Prior to the interview, program managers will be provided a copy of the questions to be asked from a standard script created by the research team. Each question is formatted in multiple choice, e.g., “How long has the program been in existence?” [1: Less than 1 year; 2: 1-3 years; 3: 3-5 years; 4: 5-10 years; 5: 10 or more years; 6: Don’t know]. Using this method, program managers will provide unambiguous answers to data points not collected by record abstraction.

Step 3: Establishing reliability and validity. Data collected via interview/survey and abstraction are subject to bias that may result from rater subjectivity.¹⁰⁴ In order to determine the agreement between the two evaluators, a baseline reliability evaluation will be conducted early in the process to calculate inter-rater reliability. In order to determine validity of self-reported data from the PSAT, agreement between self-reported, record-based information, and interview/survey information will be assessed. Both inter-rater reliability and validity of self-reported data will be checked at baseline and two other time points.

Phase 3 (Aim 3):

C.7. (Aim 3): Actively disseminate The Program Sustainability Action Planning Model and Training Curriculum materials and study results to support future adoption.

[figure not shown]
No treatment with intervention or comparison groups will take place during this phase.

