9.0 Statistical Considerations

C.6.d Statistical power

To estimate the sample size needed for the study, an a priori power analysis was performed using data from a natural experiment. The data consists of Pre and Post PSAT averages from previous work with five tobacco control programs that received action planning and training, and five programs that did not receive action planning or training for which pre- and post-PSAT scores are available. To determine effect size, t-tests of differences-in-means were conducted for the two groups using the changes in PSAT scores between the Pre and Post PSAT data. The standardized differences and t-statistics yielded an effect size of 1.25, which is a large effect size according to Cohen's criteria.¹⁰⁷ Using R statistical environment with packages from Del Re¹⁰⁸ and Champely,¹⁰⁹ the effect size with power = 0.8 and $\alpha = 0.05$ project the necessary sample size to be approximately 9 (programs) per group. Since these calculations are based on a natural experiment, which we note occurred over a period of time that also saw changes to the recommended action planning,² we are careful not to overstate the anticipated power and therefore conservatively propose a sample size one-third larger than calculated, 12 per group as shown in Figure 4. This sample is also sufficient to measure the main goal of the study, to discern whether the training, and accompanying PSAT tool, significantly increase institutionalization of state TC programs.^{108–110}

C.6.e. Data analyses. Descriptive statistics will be calculated (e.g., frequencies and measures of central tendency and dispersion), for both the intervention and comparison group at each of the three data collection time points to assess baseline averages and changes. Multiple comparisons across groups and times will be drawn for independent and dependent variables. All continuous measures will be examined for non-normality and all relationships will be examined for linearity where applicable. Strategies for addressing issues encountered will be applied as necessary such as different functional forms, category scaling, and robust error calculations. In addition, the dose reception and delivery, and participant measures from Aim 1 (C.5.d.) will be used to calculate rates of adoption and implementation of training recommendations (intervention states) and other potential actions taken (comparison states, C.5.e).

[figure not shown]

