To incorporate the influence of idiosyncratic characteristics of the state programs, longitudinal regression analysis will be used to model the outcome for each of the dependent variables. This analysis is modeled in Equation 1.

$$\beta_0 + \beta_1 PSAT_{i,t=0} + \beta_2 G_i + \beta_3 D_{it} + \beta_4 (G_{it} * D_{it}) + B_{5-k} X_{it} = Y_{it}$$

Equation 1

where i = state, t = time 1 or 2, $PSAT_{i,t=0}$ = baseline PSAT score, G_i = group (intervention or comparison), D_{it} = dose variable, $(G_{it} * D_{it})$ = an interaction between the group and dose terms, X_{it} = a vector of programmatic, organizational, community and funder variables, and Y_{it} = the

Figure 4. Sample size and power calculation

outcome variable. This analysis will ultimately be used to test Hypothesis 1, that the impact of the training is nonzero and positive.

$$H_0: \hat{\beta}_{intervention} = 0 \quad H_a: \hat{\beta}_{intervention} > 0$$

Hypothesis 1

The multivariate approach allows us to account for the numerous influences found in programmatic, organizational, community, and funder attributes. Data collection at different time points also allows for measuring changes in these variables, and the influence these changes have on institutionalization outcomes. In addition, the level of adoption and implementation of action plans both from the training (intervention states) and from other initiatives (comparison states) will vary across programs and time. Varying levels of action plan implementation across states must be acknowledged. Multivariate longitudinal analyses also allow us to control for differing degrees of dosage reception and delivery. We have successfully used similar dose variables.^{111,112}

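### Consider adding each record or interview outcome's own baseline to Equation 1: it is collected in all 24 states, but the only explicit baseline term is PSAT

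*Combined protocol and SAP*

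**What the plan says.** Section 9.0 (C.6.e Data analyses) sets out Equation 1 as the general model: "longitudinal regression analysis will be used to model the outcome for each of the dependent variables". Its definitions open with "where i = state, t = time 1 or 2", so Y_it and the covariate vector X_it are follow-up values as written. The only term fixed at t = 0 is PSAT. The definitions list "baseline PSAT score, G_i = group (intervention or comparison", then the dose variable, the group-by-dose product and X_it, whose members are not named.

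Section 5.1 collects the other outcome sources before follow-up. For records: "A review and abstraction of state level TC program public records will be performed for all 24 states at three time points- baseline", and again in years 2 and 3. For the manager interview and survey: "These will be performed for all 24 states at three time points- baseline and in June during years 2 and 3".

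Baseline values do have other uses. C.6.e plans descriptive statistics at each of the three time points and adds "Multiple comparisons across groups and times will be drawn for independent and dependent variables". The text after Hypothesis 1 says "Data collection at different time points also allows for measuring changes in these variables, and the influence these changes have on institutionalization outcomes", where the variables meant are program, organizational, community and funder attributes. Neither statement puts the outcome at t = 0 into the model that tests Hypothesis 1.

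**The concern.** Section 5.1 (Aim 2) describes the dependent variable in terms of institutionalization and sustainability, and names program records as a data source. The power paragraph in Section 9.0 treats institutionalization as the main goal. Section 10.0 gives funding, staff numbers and program size as examples of abstracted variables. Such measures could well persist from year to year, although the documents give no correlations. If they do, differences between states that existed at the start stay in the residual unless baseline PSAT or X_it happens to absorb them.

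With 24 independent units, precision is scarce. The plan's effect size was itself derived from changes in PSAT, a quantity that uses the outcome's own baseline. The same sample is then called sufficient for institutionalization, where Equation 1 shows no such term.

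**Working it through.** **The plan's own figure.** With effect size 1.25, power 0.8 and alpha 0.05 (Section 9.0, C.6.d), a one-sided two-sample t-test needs 9 per group (power 0.814), which matches the plan. At 12 per group the power is 0.907. That calculation concerns PSAT change and does not depend on this point. The plan gives no figure for own-baseline adjustment.

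**Inputs.** N = 24 states (Section 9.0). The number k of covariates besides group is not stated. I take k = 1 (PSAT only), k = 5 (PSAT and an assumed four X_it) and k = 7 (dose and group-by-dose also counted). The partial correlation p of the outcome with its own baseline, given the other terms, is not stated either, so a range is shown. One follow-up value or mean per state is used.

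**Formula.** With q covariates, the expected variance of the group coefficient is proportional to the residual variance times 1 + q/(N - q - 3) = 21/(21 - q). Adding the own baseline multiplies the residual variance by (1 - p²) and raises q from k to k + 1. The variance ratio, with against without the term, is

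(1 - p²) × (21 - k)/(20 - k).

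Break-even is at p = √(1/(21 - k)).

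| p | k = 1 (20/19) | k = 5 (16/15) | k = 7 (14/13) |
|---|---|---|---|
| 0 | 1.053 | 1.067 | 1.077 |
| 0.2 | 1.011 | 1.024 | 1.034 |
| 0.3 | 0.958 | 0.971 | 0.980 |
| 0.4 | 0.884 | 0.896 | 0.905 |
| 0.5 | 0.789 | 0.800 | 0.808 |
| 0.6 | 0.674 | 0.683 | 0.689 |
| Break-even p | 0.224 | 0.250 | 0.267 |

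At p = 0.5 the variance falls by 21% (k = 1) to 19% (k = 7). If the own baseline predicts nothing, it rises by 5% to 8%. With k = 1, the 95% confidence interval is 2.9% wider at p = 0 and 10.9% narrower at p = 0.5.

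**Check.** In 20,000 simulated trials with k = 1, the variance ratios were 1.051, 0.796 and 0.526 at p = 0, 0.5 and 0.7. The formula gives 1.053, 0.789 and 0.537.

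**Bias through dose.** The figures above assume that dose is unrelated to the baseline outcome. Section 10.0 defines dosage received partly by how far the action plan is implemented, which could depend on where a state starts. As an illustration, assume no true effect, own-baseline correlation 0.6, within-arm correlation of dose with the baseline outcome 0.3, and dose with SD 1 and means 3 (intervention) and 1 (comparison). The dose slope without the own baseline is then 0.6 × 0.3 = 0.18, and the group coefficient shifts by -0.18 × (3 - 1) = -0.36 outcome SD. With baseline PSAT in the model (assumed correlation 0.2 with the outcome at both times), the shift is about -0.34. Adding the own baseline brings it to about zero. If dose and baseline are uncorrelated, there is no shift.

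**The case against.** The strongest reply is that nothing is broken. A randomized comparison at follow-up is valid without the own baseline, the size of any gain is unknown, and precision may be lost. That stands, and it is why this is only a suggestion.

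X_it is open-ended and could include baseline values. But it is indexed at follow-up, and nothing says that it holds the outcome at t = 0. Even if that is intended, the plan should say so before results are known.

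The text available does not show which record measures are outcomes and which are predictors. No single outcome can therefore be named as affected, and the point is limited to non-PSAT outcomes with a usable baseline. The interview items are a further limit. The plan says of them "Each question is formatted in multiple choice", so figures for a continuous outcome in a linear model may not carry over.

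The seven-covariate count is also only an assumption. If dose means hours delivered and is zero in every comparison state, the group-by-dose product equals dose and one term drops out. Then k = 6 and the cost is 15/14, or 7.1%, which is inside the range shown.

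Two stronger readings are tempting. One is that omitting the own baseline biases the trial. The documents do not support this, because randomization does not require the term and the bias illustrated above arises only if dose tracks the starting level. The opposite reading, that only precision can be at stake, is not supported either, because Equation 1 conditions on dose after randomization.

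**Conclusion.** The point holds as an inexpensive improvement. As written, Equation 1 tests record and interview outcomes without their own baseline, although that baseline is collected in all 24 states. PSAT as an outcome is not affected.

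The loss is at most about 5% in variance with PSAT as the only other covariate, and about 8% with an assumed seven. The variance falls by 19-21% at an assumed partial correlation of 0.5, and the term pays for itself above about 0.22-0.27. These figures rest on a linear model, a continuous outcome and dose unrelated to the baseline outcome.

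A reduction in bias is possible but depends on a link between dose and starting level that the documents do not establish. The stated sample size is unaffected, and a reader should not infer that the trial is underpowered from this point.

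**What to change.** For each non-PSAT outcome with a usable baseline value, add β·Y_{i,t=0} to Equation 1 and keep baseline PSAT. List these outcomes in the SAP before follow-up data are seen.

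Leave the term out only where the baseline data themselves show almost no spread between states. Implementation of the action plan, one of the examples in Section 10.0, may be such a case. This can be judged from baseline data alone.

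Baseline PSAT should stay because dropping it can forfeit the gain. Suppose PSAT is the only other covariate, the own-baseline correlation is 0.5, and PSAT correlates 0.5 with the follow-up outcome and 0.2 with its baseline. Replacing PSAT then gives a variance ratio of (1 - 0.25)/(1 - 0.25) = 1.00. Adding to it gives p = (0.5 - 0.1)/√(0.75 × 0.96) = 0.471 and a ratio of 0.778 × 20/19 = 0.82.

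The cost is one term per listed outcome, one degree of freedom and no new data collection. The change does not settle whether Equation 1 should condition on dose, which is a separate question.

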10.0 Recordkeeping

The Principal Investigator, [name], will be responsible for monitoring the data safety and quality of the overall study. This is a minimal risk study that does not warrant a formal Data Safety Monitoring Board.

Program Sustainability Assessment Tool (PSAT). The PSAT is a 40-item measure of a program's sustainability capacity which requires 10-15 minutes to complete. Individuals selected by state TC program managers will be invited to complete the PSAT online via our secure website <https://sustaintool.org/>. Data collected through the website is automatically de-identified by the website and aggregated at the state level. E-mail addresses are collected on the site, but solely for website management, technical assistance, and user access. See Appendix A for full copy.

Workshop Data Collection Form. Several process measures will be collected to assess the effectiveness of the training and support delivered. All measures will be collected via survey at the completion of each training component or tracked by review of programmatic records (i.e., action plan, meeting minutes). Quantitative data collected for this aim will be analyzed using descriptive statistics. Qualitative analysis of programmatic records will be conducted following procedures outlined. See Appendix B for full copy.

Dosage delivered is the number of units of an intervention delivered or provided.¹⁰¹ For this study, this measure will be defined by the number of hours of training and technical assistance provided to each state.

Dosage received is the extent to which participants engage with or use the materials provided.¹⁰¹ This will be measured by whether or not the action plan is completed and implemented, whether the workgroup utilizes the resources and materials provided, and the extent to which the action plan is implemented.

Participant reactions will be measured by the extent to which the participants felt that the objectives of the training and technical assistance were achieved, satisfaction with the training and technical assistance and perceived usefulness of the training provided.

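### Hypothesis 1 is tested in a model that conditions on post-assignment dose, and no coefficient is named, so the test is not the randomised arm comparison used for sizing

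*Combined protocol and SAP*

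**What the plan says.** Section 9.0 (C.6.e) gives one model, Equation 1. Its terms are baseline PSAT, group G, dose D, "an interaction between the group and dose terms", and a vector X of programme, organisational, community and funder variables, at follow-up times 1 and 2. Of this model the plan says: "This analysis will ultimately be used to test Hypothesis 1, that the impact of the training is nonzero and positive". Hypothesis 1 is stated on a parameter labelled beta with subscript intervention. Equation 1 has no such term, and none of its coefficients is assigned to it.

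Adjustment for dose is deliberate: "Multivariate longitudinal analyses also allow us to control for differing degrees of dosage reception and delivery". The same paragraph expects action-plan implementation "from other initiatives (comparison states) will vary across programs and time", and section 5.1 (Comparison state protocol) says that such implementation will be tracked and allowed for in the analysis.

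Section 10.0 defines the dose measures. For dosage delivered, "this measure will be defined by the number of hours of training and technical assistance provided to each state". For dosage received, "This will be measured by whether or not the action plan is completed and implemented", together with use of the materials and the extent of implementation.

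The sample size in C.6.d has another basis: "t-tests of differences-in-means were conducted for the two groups using the changes in PSAT scores". Section 9.0 also says "Multiple comparisons across groups and times will be drawn for independent and dependent variables", but it does not make any of these comparisons the test of Hypothesis 1.

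**The concern.** Both dose measures are part of the intervention or a consequence of it. The plan's own rationale puts them on the causal pathway. The Objectives describe action plans as the means of bringing about institutional change, and the Rationale cites evidence that having a sustainability plan predicts programme survival. The PSAT itself asks whether the programme has a sustainability plan (Appendix A, Strategic Planning, item 3), so a plan-based dose overlaps with that outcome.

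A group coefficient adjusted for such a variable leaves out whatever the training achieves through it. A training that works by getting plans made and carried out could then show a null group coefficient. Dose is not randomised, and states that implement more may differ in other ways that affect the outcome, so conditioning on it also gives up the protection of randomisation. Finally, because the tested coefficient is not named, it could be chosen after the data are seen.

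**Working it through.** **1. The plan's sample size.** Inputs from C.6.d: effect size d = 1.25, power 0.80, alpha 0.05. A two-sample t-test has 2n - 2 degrees of freedom and noncentrality d × √(n/2).

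- One-sided: n = 8.68, so 9 per group (power 0.814). This reproduces the stated 9 and agrees with the one-sided alternative in Hypothesis 1. At 12 per group the noncentrality is 1.25 × √6 = 3.06 and power is 0.907.
- Two-sided: n = 11.09, so 12 per group (power 0.833).

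The sample size is therefore sound for a dose-free comparison of two arms.

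**2. What Equation 1 estimates.** Hold baseline PSAT and X equal between arms, and let μ1 and μ0 be the mean doses in intervention and comparison states. Then:

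- mean outcome, intervention = β0 + β2 + (β3 + β4)μ1
- mean outcome, comparison = β0 + β3μ0
- arm difference = β2 + β3(μ1 - μ0) + β4μ1

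The possible readings of the intervention beta compare with this as follows.

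- β2 is the arm difference at dose zero, or at the grand mean if dose is centred there. Its value depends on a coding that the plan does not state.
- β2 + β4d, at any fixed dose d, is a difference between arms at equal dose. At d = μ1 it lacks exactly the term β3(μ1 - μ0), the part that runs through dose.
- β4 is a difference in dose slopes.

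The arm difference can be recovered by centring dose within arm, or by averaging over each arm's own dose distribution with X at baseline. The plan specifies neither.

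**3. A conditional point on identification.** If D were hours only and constant at c in comparison states, then G×D = D - c + cG. This is an exact linear combination of other terms, so β3 and β4 could not be separated. The expected variation in comparison states suggests an implementation-type dose instead.

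**4. Illustration of size.** The documents give neither dose distributions nor a mediated share, so these are assumptions. There are 12 v 12 states and one follow-up. Dose is normal with arm means D1 and D0 and a common SD. The outcome is Y = direct×G + slope×D + error, with slope = share × 1.25/(D1 - D0), direct = (1 - share) × 1.25, and residual variance 1 - (slope × SD)². The within-arm SD of Y is then 1 and the total effect 1.25 in every case. There is no true interaction and no common cause of dose and outcome. The fit is OLS on G, D and G×D (20 df), one-sided 5%, with 20,000 replicates and a Monte Carlo SE of at most 0.35 points. The expected β2 is (1 - share) × 1.25, that is 0, 0.31, 0.63, 0.94 and 1.25 across the columns below.

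Rejection rates (%) by share of the effect that runs through dose:

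| Implementation, quantity tested | 100% | 75% | 50% | 25% | 0% |
|---|---|---|---|---|---|
| 70 v 20 (SD 15), β2 uncentred | 4.9 | 7.8 | 10.2 | 14.5 | 19.5 |
| 70 v 20, β2 grand-mean centred | 5.0 | 10.0 | 17.9 | 28.0 | 40.5 |
| 70 v 20, β2 + β4 × mean intervention dose | 5.0 | 8.7 | 14.0 | 21.3 | 29.6 |
| 60 v 30 (SD 20), β2 uncentred | 5.0 | 9.6 | 14.5 | 20.8 | 28.2 |
| 60 v 30, β2 grand-mean centred | 5.0 | 17.7 | 34.8 | 53.8 | 72.1 |
| 60 v 30, β2 + β4 × mean intervention dose | 4.9 | 15.4 | 28.8 | 44.5 | 61.0 |

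The arm comparison (t-test, 22 df) rejects in 90-91% of replicates in all ten cases. β4 rejects in 4.7-5.2%, as it should with no true interaction. The 0% column shows that power falls even when nothing runs through dose, because group and dose are correlated. With dose centred within arm, the mean of β2 is 1.25 throughout. Its model SE falls from 0.40 to 0.22 as the share rises, while the estimate's actual SD stays at 0.41, because the arm mean doses are treated as fixed.

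**The case against.** **Overlap of dose.** Section 1.0 says that all awarded states must develop a sustainability plan, and comparison states receive the webinar, the PSAT report, recommendations and a resource packet. The arms may overlap in dose more than assumed above. At 60 v 45 (SD 20), grand-mean-centred β2 rejects in 72% and 84% with 25% and 0% of the effect through dose. At 55 v 40 (SD 25) it rejects in 77% and 86%. The lowest figures also need strong assumptions: at 60 v 30 with everything through dose, dose explains (1.25 × 20/30)² = 69% of within-arm variance. This stands. The loss of power may be modest and should not carry the argument.

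**Simplified model.** The illustration omits baseline PSAT, X and the second follow-up, and the uncentred rows evaluate the contrast at zero implementation. This is true, but the algebra in step 2 does not depend on it.

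**Natural reading.** G is defined as group, so β2 is the obvious candidate for the intervention beta. Even so, β2 is a dose-conditional effect.

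**Dose-free comparisons are already planned.** They are, but they are general, and the plan gives the test of Hypothesis 1 to Equation 1.

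**Details elsewhere.** Section 9.0 refers to C.5.d and C.5.e, which are not in the document, and it does not say which dose measure is D. Those sections might settle D and its coding. Both measures in section 10.0 arise after assignment in any case.

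**Conclusion.** The concern holds and should be corrected before analysis. Followed as written, the test of Hypothesis 1 conditions on variables that the training is meant to change, and the tested parameter is undefined. It need not estimate the difference between intervention and comparison states, which section 5.1 (Aim 2) gives as the purpose of the randomised trial and on which the sample size rests. This follows from the equation and the dose definitions alone.

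The size of the consequence is uncertain. Under the assumed scenarios, the grand-mean-centred group coefficient has anything from 5% to 86% power, against 90-91% for the arm comparison. Where it falls depends on the mediated share and on how far dose separates the arms, and the documents give neither. A common cause of dose and outcome, which these scenarios leave out, would add bias.

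A further conditional point concerns X, which carries a time index and is not listed in section 9.0. If follow-up values of variables affected by training enter it, they could remove more of the effect.

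**What to change.** - Define the intervention beta as the coefficient of randomised group in a model without D, G×D or follow-up values of X, with states analysed as assigned.
- Adjust for baseline PSAT (or the baseline value of the outcome), the quadrant within which states are randomised (section 3.0) and time. Allow for repeated measures within state, since each contributes two follow-ups.
- State the outcome and the time point or points to which the test applies. Otherwise some choice remains after the data are seen.
- Do not adjust this test for plans that comparison states start themselves. This changes the intention in section 5.1, so the sponsor should record it as a decision about the effect to be estimated.
- Keep Equation 1 as a secondary, non-randomised dose-response analysis. State which measure is D, how it is centred, and which variables at which time points form X.

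The cost is SAP wording only. No new data or states are needed, and 12 per group still gives power of 0.907 one-sided (0.833 two-sided) for d = 1.25.
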